## 1. RATIONALE

Diabetes mellitus and its sequelae are a major and growing public health problem. The prevalence of diabetes worldwide is 194 million persons, or 5.1% of the population, and is projected to increase to 333 million, or 6.3% of the population, by 2025 (1). The number of persons with impaired glucose tolerance is estimated to increase as well. Diabetes is related to obesity, inactivity, population growth, and aging. In addition, diabetes is recognized as a group of metabolic disorders characterized by hyperglycemia and glucose intolerance due to insulin deficiency, impaired effectiveness of insulin action, or both (2).

Lifestyle strategies that include dietary modification, such as consumption of a plant-based diet, are well recognized in disease prevention and may improve type 2 diabetes (3,4). Various components of a plant-based diet may contribute to its beneficial health effects, but there has been keen interest in the possibility that plant polyphenols may have a role. Blueberries are dietary sources of polyphenols, specifically anthocyanins. Anthocyanins consist of approximately 35 – 74% of total phenolic compounds in blueberries, followed by hydroxycinnamic acid derivatives, flavonols, and flavanols (5).

There is encouraging pre-clinical evidence that berries may improve glucose management. Bilberry extract ameliorated hyperglycemia and insulin sensitivity in type 2 diabetic mice (6). Blueberry extract also reduced plasma glucose 6 h after ingestion in mice (7). Blueberry polyphenols stabilized in soybean flour reduced glucose intolerance in mice and decreased glucose production in rat hepatocytes (8). Further, lowbush blueberry extracts were found to induce beta-cell proliferation in vitro (9).

Several promising human studies have also been conducted. In healthy males, a meal with lingonberry powder plus yogurt produced an equivalent post-prandial glucose response as a meal with only yogurt, despite the extra sugar contained in the lingonberry powder containing meal (10). In another study, various berries, including strawberries, bilberries, lingonberries, and chokeberries, reduced insulin response after a meal containing berries plus bread (11). In the same study, strawberries and mixed berries also reduced glucose response after the berry-bread meal (11). In a third study, a mix of bilberries, blackcurrants, cranberries, and strawberries decreased the post-prandial glucose response in healthy adults (12).

More broadly, to date there are few clinical trials evaluating the beneficial health effects of blueberries in populations with type 2 diabetes. Four randomized parallel design studies have reported that consumption of blueberries may beneficially affect early biomarkers of cardiovascular disease and diabetes, such as altering blood pressure, insulin sensitivity and oxidative stress (13-16). A systematic review has also concluded that there is a lack of clinical trials evaluating blueberry consumption in humans with type 2 diabetes (17).

## 2. OBJECTIVE

A. Research question to be addressed (Objective)

How does highbush blueberry polyphenol consumption affect cardiometabolic parameters in males with type 2 diabetes?

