### **4. METHODS:**

#### **A. Procedures**

**Treatment.** Participants will be randomly assigned to one of two treatment groups; either 1) 22 g of a control blueberry placebo treatment (matched in energy and carbohydrate content to the blueberry treatment; ingredients are maltodextrin, fructose, artificial blueberry flavoring and coloring, citric acid and silica dioxide) along with their free-living diet per day, 2) 22 g of a freeze-dried whole blueberry powder treatment along with their free-living diet per day. One cup of fresh blueberries is equivalent to approximately 22 g of freeze-dried whole blueberry powder. This amount was chosen as it is a reasonable amount of fruit for subjects with type 2 diabetes to consume. Subjects will be asked to consume 11 g of freeze dried blueberry powder or placebo, reconstituted with 240 ml water, with their morning and evening meals for 8 weeks. Participants will be counseled by a registered dietitian as to how the treatment is to be consumed, and compliance will be monitored by a daily questionnaire. In addition, the number of used and unused treatment packets will be tracked. Subjects will receive a 4 week supply of these products during a visit to the Stratton VA Medical Center. Treatments will be blinded to the study investigators and subjects (e.g., investigators and subjects will not know the composition of the treatments until after the study is complete). The US Highbush Blueberry Council will hold the code to the study treatments.

Subjects will be responsible for their own meals and will continue to follow their typical pattern of food intake (food consumption will be monitored periodically as described below).

**General Physiological Variables.** Body weight will be determined following an 8-h fast. Height will be measured with participants positioned in the Frankfort frontal plane. Each subject's height without shoes will be measured to the nearest 0.1 cm with a wall-mounted stadiometer. Waist and hip circumferences will be collected according to standard protocols. Body weight and composition, and waist/hip circumference will be obtained at baseline, at 4 weeks, then after 8 weeks of the study. These measurements require 30 minutes for the entire study.

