Blood pressure will be collected according to a standard protocol. Subjects will be taken to a quiet room with subdued lighting. The appropriate size cuff will be attached to the upper right arm according to the manufacturer's instructions. Blood pressure will be measured three times with a Dinamap Compact Blood Pressure Monitor, which will be programmed to take an initial reading and then a reading after 5 minutes and after 10 minutes. The arm will be adjusted so that the height of the upper arm is level with the heart. Subjects will have both feet flat on the floor. Subjects

will be instructed to refrain from consuming coffee for at least 30 minutes prior to the measurement and will be advised to empty their bladder prior to the measurement. Blood pressure will be obtained at baseline, at 4 weeks, then after 8 weeks of the study. Each measure requires 20 minutes (20 minutes x 3) = 1 hour for the entire study.

**Blood Collection.** Twice during the study, at baseline and after the 8-week treatment period, 25 ml of blood will be collected from the antecubital veins of subjects following an overnight fast. A total of 50 ml of blood will be collected. Plasma and serum will be collected then analyzed. Plasma and serum will be used for analysis of health indices and biomarkers of cardiovascular disease and diabetes (cardiometabolic parameters). Blood will be analyzed for a complete metabolic panel, blood lipids, lipoproteins and inflammation (triglycerides, total cholesterol, HDL cholesterol, LDL cholesterol, and high sensitivity CRP) along with markers of glucoregulatory mechanisms (hemoglobin A1C, fructosamine, insulin, and glucose). Each blood draw requires 20 minutes, (20 minutes x 3) = 1 hour for the entire study.

**Urine Collection.** Twice during the study, at baseline and after the 8-week treatment period subjects will provide a urine sample of at least 10 ml. Urine will be collected in plastic containers and will be stored on ice during collection and until samples can be delivered to the laboratory. Each urine collection requires 5 minutes, (5 minutes x 2) = 10 minutes for the entire study. Urine will be analyzed for urine microalbumin to creatinine ratio.

**Questionnaires.** Participants will be asked to complete a daily questionnaire regarding their general health; if they consumed any over the counter or prescription medications and their general feeling of well-being.

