#### D. Data analysis and sample size justification

Data analysis:

The data will be analyzed using a mixed model in order to partition variance from random and fixed effects. The model will account for age, BMI and the significance for other terms will be tested to determine if they are to remain in the model. Some terms may be used as covariates. Split-plot and split-split plot analysis will be used to partition variances from measurements for which there are repeated measures. Contrasts statements or appropriate multiple comparisons of means will be completed using least-square means.

Sample size:

Sixty males with type 2 diabetes will be recruited for the study. The sample size for this study is based on a standard deviation from a previous study conducted by Basu et al (13), which showed that 50 g of freeze-dried blueberry powder lowered systolic and diastolic blood pressure. A sample size calculation was estimated for a 1-factor ANOVA for a parallel-arm study with > 80% power to detect a significant difference. Twenty-four participants per group are needed, and 30 per group are determined based on a 20% drop out rate.

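### No primary outcome is designated and no error control across outcomes is stated; blood pressure is implied as the lead outcome but never declared

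*Combined protocol and SAP*

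**What the plan says.** Section 2 gives one objective: "How does highbush blueberry polyphenol consumption affect cardiometabolic parameters in males with type 2 diabetes". It is an open plural, and no section of the combined protocol and SAP labels any outcome primary or secondary.

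Section 4.A attaches the same term to the blood work: "Plasma and serum will be used for analysis of health indices and biomarkers of cardiovascular disease and diabetes (cardiometabolic parameters"). It continues: "Blood will be analyzed for a complete metabolic panel, blood lipids, lipoproteins and inflammation". Nine markers are named: triglycerides, total, HDL and LDL cholesterol, high-sensitivity CRP, HbA1c, fructosamine, insulin and glucose. The analytes of the metabolic panel are not listed. The same section adds blood pressure, a urine measure ("Urine will be analyzed for urine microalbumin to creatinine ratio") and, under General Physiological Variables, weight, composition, waist and hip.

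The schedules differ:
- Blood: "Twice during the study, at baseline and after the 8-week treatment period, 25 ml of blood will be collected". Urine follows the same two visits.
- Blood pressure: "Blood pressure will be obtained at baseline, at 4 weeks, then after 8 weeks of the study".
- Body measures: "Body weight and composition, and waist/hip circumference will be obtained at baseline, at 4 weeks, then after 8 weeks of the study".

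Section 4.D specifies a mixed model and says "Split-plot and split-split plot analysis will be used to partition variances from measurements for which there are repeated measures". It also provides for contrasts, or suitable multiple comparisons, of least-square means. For sample size it uses a standard deviation from a study in which blueberry powder lowered systolic and diastolic pressure. It states power above 80% for a significant difference, without naming the outcome, and arrives at 24 per group, raised to 30 for dropout. No significance level is stated.

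**The concern.** With at least 12 measured outcomes, no ranking and no rule for reading them together, the plan as written would allow an unadjusted p<0.05 in any one of them to be reported as the answer to the objective. Nothing says which result the stated power belongs to. For blood pressure and the body measures, the repeated-measures analysis puts weeks 4 and 8 in one model but does not say whether the overall, week 4 or week 8 contrast decides. A primary outcome chosen after unblinding would not be credible, so the gap cannot be repaired at the reporting stage.

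**Working it through.** **The plan's own figure.** Section 4.D: 24 / (1 - 0.20) = 30 per group, which reproduces. The 24 itself cannot be checked, because no standard deviation, target difference, significance level or sidedness is given. At 80% power and an assumed two-sided 0.05, it implies a standardised difference of (1.960 + 0.842) x sqrt(2/24) = 0.81 by the normal approximation, or 0.83 by the two-sample t test.

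**Inputs for the false-positive illustration.**
- From Section 4.A: 5 lipid and inflammation markers + 4 glucoregulatory markers = 9. Adding systolic pressure, diastolic pressure and the urine ratio gives 12.
- Assumed: two-sided 0.05 per outcome, no true effect, one test per outcome, and a common correlation r between outcomes. The plan gives neither a significance level nor correlations, so a wide range of r is shown.
- Not counted: the unlisted panel analytes, and the body measures, which the plan does not say will be tested for effect.

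**Formulas for k outcomes.**
- Independent: 1 - 0.95^k. For k = 9 this is 1 - 0.630 = 0.370; for k = 12 it is 1 - 0.540 = 0.460; for k = 2 it is 1 - 0.9025 = 0.0975.
- Common correlation r: 1 - E{[Phi((c - sqrt(r)U)/sqrt(1-r)) - Phi((-c - sqrt(r)U)/sqrt(1-r))]^k}, with U standard normal and c = 1.96, integrated numerically.

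Chance of at least one false positive:

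| Outcomes tested | r = 0 | r = 0.5 | r = 0.7 | r = 0.9 |
|---|---|---|---|---|
| 9 blood markers | 37.0% | 26.9% | 20.2% | 12.4% |
| 12 (plus two pressures, urine ratio) | 46.0% | 31.9% | 23.2% | 13.5% |
| 2 pressures only | 9.8% | 9.1% | 8.3% | 7.0% |

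A simulation of two-sample t tests with 24 per arm (100,000 runs, nine markers) gave 36.8%, 27.4% and 20.3% at r = 0, 0.5 and 0.7, in agreement with the first row. One designated primary outcome with one contrast would carry 5%.

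**Power cost of adjusting secondaries.** Take 24 per group and a standardised difference of 0.826, which gives 80% power at 0.05. At the first Holm step over nine outcomes, 0.05/9 = 0.0056, power is 48.8%. That is close to the worst case. In simulation, Holm power per outcome is about 51% if three of the nine have that effect and about 61% if all nine do.

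**The case against.** The strongest reply is that blood pressure is the implied lead. It is the only outcome mentioned in the sample-size paragraph, and Section 1 counts it among the early biomarkers of cardiovascular disease and diabetes, close to the description that Section 4.A gives of cardiometabolic parameters. This stands as far as it goes. A reader might infer that the trial has no lead outcome at all and that its false-positive risk is simply the nine-marker figure; the documents do not support that. If the two pressures were co-leads, the figure is 7-10%. But the implication is not a declaration. The text does not choose systolic or diastolic pressure, does not say whose standard deviation was used, and does not tie the power to either.

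A second reply is that Section 4.D already provides for multiple comparisons. The wording does not strictly confine these to one outcome. However, comparisons of least-square means are most naturally read as within one outcome's model, and no method is named.

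A third is that the time-point gap is narrow. That is correct: blood and urine have week 8 as their only post-baseline value, so the gap concerns blood pressure and body measures alone.

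A fourth is that the objective is an open question in a small dietary study, so formal control over every secondary outcome is partly a matter of preference. This is fair, and the fix allows an exploratory label. But the plan never calls itself exploratory, and a power statement needs a named target.

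**Conclusion.** The concern holds. No primary outcome is designated, no error control across outcomes is stated, and no decisive visit is named for the measures taken at both weeks 4 and 8. Blood pressure is implied as the lead without being declared. It should be fixed before unblinding.

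The size depends on assumptions that the plan neither supplies nor excludes: two-sided 0.05, no true effect, one test per outcome and a common correlation. On those terms the chance of at least one false positive runs from 37% down to 12% over the nine blood markers and from 46% down to 13% over 12 outcomes, as the correlation goes from 0 to 0.9. Every value exceeds 5%, but nothing in the documents singles out one of them.

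A reader might also infer that no result, positive or null, could be judged against the design. That goes too far: at 80% power and two-sided 0.05, 24 per group corresponds to a standardised difference of about 0.83 whichever outcome is used. What is missing is the ranking of outcomes and the link between the stated power and one of them.

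**What to change.** Before unblinding, amend Sections 2 and 4.D to:

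1. Name as the single primary outcome the one whose standard deviation set the sample size. The sponsor should confirm which that was, for example systolic or diastolic pressure.
2. Name the between-arm contrast at week 8 as decisive, tested at two-sided 0.05. Week 8 is the only post-baseline visit shared by all the listed measures.
3. Declare all other outcomes, and the week 4 values, secondary or exploratory. Report them with confidence intervals and make no claim of effect from an isolated unadjusted p<0.05. If claims on secondaries are wanted, list the set and apply Holm across it.

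The cost is that an isolated secondary result can no longer be claimed. Under Holm over nine outcomes, first-step power at a standardised difference of 0.83 falls from 80% to about 49%; the exploratory route avoids that loss but permits no claim. Visits and assays do not change, and the primary keeps its full 0.05.

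The sample size is unchanged provided the sizing outcome is the primary. If another is chosen, the power that 24 per group gives for it should be restated, and wording alone may not be enough. For instance, at an assumed standardised difference of 0.5, 24 per group gives about 40% power, and 80% would need about 64 per group.

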### **3. STUDY DESIGN:**

Sixty males (BMI  $>25$  kg/m $^2$ ) with type 2 diabetes will be recruited to enroll in a placebo-controlled, double-blind, randomized parallel arm study with 2 treatment groups for a total of 8 weeks.

### **4. METHODS:**

#### **A. Procedures**

**Treatment.** Participants will be randomly assigned to one of two treatment groups; either 1) 22 g of a control blueberry placebo treatment (matched in energy and carbohydrate content to the blueberry treatment; ingredients are maltodextrin, fructose, artificial blueberry flavoring and coloring, citric acid and silica dioxide) along with their free-living diet per day, 2) 22 g of a freeze-dried whole blueberry powder treatment along with their free-living diet per day. One cup of fresh blueberries is equivalent to approximately 22 g of freeze-dried whole blueberry powder. This amount was chosen as it is a reasonable amount of fruit for subjects with type 2 diabetes to consume. Subjects will be asked to consume 11 g of freeze dried blueberry powder or placebo, reconstituted with 240 ml water, with their morning and evening meals for 8 weeks. Participants will be counseled by a registered dietitian as to how the treatment is to be consumed, and compliance will be monitored by a daily questionnaire. In addition, the number of used and unused treatment packets will be tracked. Subjects will receive a 4 week supply of these products during a visit to the Stratton VA Medical Center. Treatments will be blinded to the study investigators and subjects (e.g., investigators and subjects will not know the composition of the treatments until after the study is complete). The US Highbush Blueberry Council will hold the code to the study treatments.

Subjects will be responsible for their own meals and will continue to follow their typical pattern of food intake (food consumption will be monitored periodically as described below).

**General Physiological Variables.** Body weight will be determined following an 8-h fast. Height will be measured with participants positioned in the Frankfort frontal plane. Each subject's height without shoes will be measured to the nearest 0.1 cm with a wall-mounted stadiometer. Waist and hip circumferences will be collected according to standard protocols. Body weight and composition, and waist/hip circumference will be obtained at baseline, at 4 weeks, then after 8 weeks of the study. These measurements require 30 minutes for the entire study.

Blood pressure will be collected according to a standard protocol. Subjects will be taken to a quiet room with subdued lighting. The appropriate size cuff will be attached to the upper right arm according to the manufacturer's instructions. Blood pressure will be measured three times with a Dinamap Compact Blood Pressure Monitor, which will be programmed to take an initial reading and then a reading after 5 minutes and after 10 minutes. The arm will be adjusted so that the height of the upper arm is level with the heart. Subjects will have both feet flat on the floor. Subjects

will be instructed to refrain from consuming coffee for at least 30 minutes prior to the measurement and will be advised to empty their bladder prior to the measurement. Blood pressure will be obtained at baseline, at 4 weeks, then after 8 weeks of the study. Each measure requires 20 minutes (20 minutes x 3) = 1 hour for the entire study.

**Blood Collection.** Twice during the study, at baseline and after the 8-week treatment period, 25 ml of blood will be collected from the antecubital veins of subjects following an overnight fast. A total of 50 ml of blood will be collected. Plasma and serum will be collected then analyzed. Plasma and serum will be used for analysis of health indices and biomarkers of cardiovascular disease and diabetes (cardiometabolic parameters). Blood will be analyzed for a complete metabolic panel, blood lipids, lipoproteins and inflammation (triglycerides, total cholesterol, HDL cholesterol, LDL cholesterol, and high sensitivity CRP) along with markers of glucoregulatory mechanisms (hemoglobin A1C, fructosamine, insulin, and glucose). Each blood draw requires 20 minutes, (20 minutes x 3) = 1 hour for the entire study.

**Urine Collection.** Twice during the study, at baseline and after the 8-week treatment period subjects will provide a urine sample of at least 10 ml. Urine will be collected in plastic containers and will be stored on ice during collection and until samples can be delivered to the laboratory. Each urine collection requires 5 minutes, (5 minutes x 2) = 10 minutes for the entire study. Urine will be analyzed for urine microalbumin to creatinine ratio.

**Questionnaires.** Participants will be asked to complete a daily questionnaire regarding their general health; if they consumed any over the counter or prescription medications and their general feeling of well-being.

Study Application (administered once) – 30 minutes- to determine eligibility  
Health History (administered once) – 30 minutes- to determine eligibility  
Three-Day Food Record (2 weekdays and 1 weekend day; administered 8 times) – 20 minutes per record, (20 minutes x 8) = 2 hours 40 minutes  
Daily Questionnaire (administered for 56 days) – 5 minutes per questionnaire (5 minutes x 56) = 4 hours 40 minutes

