#### Exclusion Criteria:

- Use of insulin
- Presence of chronic kidney disease (GFR  $\leq 45 \text{ mL/min}$ ), liver cirrhosis, gastrointestinal disease, pancreatic disease, or malabsorption syndromes
- Weight loss of  $>10\%$  of body weight over the last 6 months; routine participation in heavy exercise
- Heavy smokers ( $>20$  cigarettes per day)
- Unable or unwilling to give informed consent or communicate with study staff
- Other medical, psychiatric, or behavioral factors that in the judgment of the Principal Investigators may interfere with study participation or the ability to follow the intervention protocol
- Allergies to blueberries or blueberry products

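### Neither arm is asked to limit blueberries, although the active dose is about one cup of ordinary fruit, so placebo men may reach that dose within protocol and the contrast could be diluted

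*Combined protocol and SAP*

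**What the plan says.** Section 2 states the question as "How does highbush blueberry polyphenol consumption affect cardiometabolic parameters in males with type 2 diabetes".

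Section 4.A (Treatment) sets the dose in food terms: "One cup of fresh blueberries is equivalent to approximately 22 g of freeze-dried whole blueberry powder". It gives the reason as "This amount was chosen as it is a reasonable amount of fruit for subjects with type 2 diabetes to consume". Both arms take their powder with a free-living diet, and "Subjects will be responsible for their own meals and will continue to follow their typical pattern of food intake". The same sentence adds in brackets that "food consumption will be monitored periodically as described below".

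The monitoring instrument, listed under Questionnaires in 4.A, is a "Three-Day Food Record (2 weekdays and 1 weekend day; administered 8 times"). The daily questionnaire is described separately: "Participants will be asked to complete a daily questionnaire regarding their general health", plus medications and well-being. The Treatment paragraph also uses a daily questionnaire for compliance. No item on berry intake is listed.

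The only blueberry-related eligibility criterion is the exclusion "Allergies to blueberries or blueberry products". Habitual intake is not a criterion, and no run-in or washout is described. Section 4.D names age and BMI for the model, leaves other terms to significance testing, and states no use for the food records. No polyphenol marker is listed among the blood or urine measurements.

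**The concern.** When the test product is a concentrated form of an everyday food, the control arm can obtain it from a shop. Here the whole daily dose is one ordinary portion. A placebo man who eats a cup of blueberries a day is exposed to roughly what the active arm receives, and the protocol tells him to carry on as usual.

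What is at stake is the exposure contrast that the stated polyphenol question depends on. Two routes could reduce it:

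- **Flattening response.** If a second cup adds less than the first, a man who already eats blueberries gains less from the active powder, even when such men are balanced between arms.
- **Differential change.** If placebo men eat more blueberries than active men during follow-up, the net difference in dose falls.

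A third effect needs neither condition: uneven blueberry intake between men adds outcome variance.

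The trial has little reserve against any of these, since 24 evaluable men per arm can detect only a difference of about 0.8 SD.

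**Working it through.** **Inputs from the documents.** 24 evaluable per group, more than 80% power, 20% dropout, 30 enrolled per group (4.D); active dose 22 g a day, about one cup (4.A).

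**Inputs assumed.** Two-sided alpha 0.05 and power of exactly 80%, because 4.D gives no alpha, detectable difference or SD value. Background blueberry intake and the shape of the dose-response are also assumed, because neither is given.

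**1. The plan's own figure.** The dropout step reproduces: 24 / (1 − 0.20) = 30 per group, 60 in total. The 24 itself cannot be reproduced without the missing inputs. Solving backwards with a two-sample t-test gives an implied standardised difference d = 0.826 (0.81 with the normal approximation).

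**2. Balanced intake, effect levels off at one cup.** If a share c of men in each arm already eat a cup a day, they gain nothing from the powder, so the mean contrast is d(1 − c). With the SD held fixed:

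| c | d(1 − c) | Power at 24 per arm |
|---|---|---|
| 0 | 0.826 | 80% |
| 5% | 0.785 | 76% |
| 10% | 0.744 | 71% |
| 20% | 0.661 | 61% |

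**3. Balanced intake, gradual flattening.** Take E(x) = x / (x + ED50), with ED50 of 11, 22 or 44 g. A man who already eats a cup gains E(44) − E(22) instead of E(22):

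- ED50 = 11: (0.800 − 0.667) / 0.667 = 0.20
- ED50 = 22: (0.667 − 0.500) / 0.500 = 0.33
- ED50 = 44: (0.500 − 0.333) / 0.333 = 0.50

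If 10% of men eat a cup a day and the rest eat none, the retained contrast is 0.9 + 0.1 × ratio = 0.92, 0.93 or 0.95. Power is then about 73% to 76%.

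Spreading the same mean (0.1 cup a day) evenly over all men would give 0.78, 0.87 or 0.92. That is a harsher assumption, because the contrast E(22 + x) − E(x) is convex in x, so uneven intake with the same mean loses less.

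**4. Balanced intake, linear response.** The mean contrast is unchanged. If a share c in each arm eat an extra cup, the variance rises by d²c(1 − c), in units of SD², and the effective d is d / √(1 + d²c(1 − c)):

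- c = 10%: 0.826 / √1.061 = 0.802, power 78%
- c = 20%: 0.826 / √1.109 = 0.784, power 76%
- c = 30%: 0.826 / √1.143 = 0.773, power 75%

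This assumes that the planning SD does not already include such dietary variation.

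**5. Differential intake.** One extra cup a week in placebo men only, with a linear response, gives c = 1/7 and power of about 67%. This shows sensitivity; it is not a forecast.

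**The case against.** The case against is substantial, and much of it stands.

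- **Randomisation balances background intake.** A reader might infer that unrestricted blueberries necessarily shrink the contrast. The documents do not support that: step 4 shows no loss of mean contrast under a linear response, and the documents give no dose-response. The only other blueberry dose in 4.D is the 50 g of the cited study, which does not show a ceiling at 22 g.
- **A between-arm drift is unlikely.** Placebo and active powders are both blueberry-flavoured and the trial is double-blind, so any tendency to drop or add berries should act on both arms alike. The instruction to keep the usual diet also discourages new habits. This stands, and it makes differential change the weaker of the two routes.
- **Intake is recorded.** A reader might also infer that a null result could not be told apart from contamination. That goes too far: eight three-day records give up to 24 recorded days per man, from which blueberry intake by arm can be examined. The remaining gap is that 4.D states no use for them. Describing intake afterwards would also not restore a contrast already lost.
- **Adding a cup-equivalent to the usual diet is a coherent question.** This is true, and restricting blueberries changes the question slightly. But section 2 asks about polyphenol consumption, and a cleaner contrast serves that question better.
- **Other berries also carry polyphenols.** Section 1 cites effects of several of them, so avoiding blueberries alone leaves some overlap. This is a reason to report other berry intake too.

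**Conclusion.** The omission is real: the plan permits control-arm exposure up to the active dose and neither limits it nor says how it will be examined. The consequence is conditional and of unknown size. It needs a flattening response or a differential change to reduce the mean contrast; otherwise the cost is added variance.

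Under the assumptions above, power at 24 per arm falls from 80% to between 76% and 61% if the effect stops at one cup and 5% to 20% of men already eat that much. It falls to about 73% to 76% under a gradual plateau with 10% of men eating a cup a day, and to 75% to 78% from variance alone with 10% to 30% doing so. If few men eat blueberries regularly, the loss is small. The point is worth acting on because prevention is cheap and has to be in place before the men start treatment. The intervention dose is not in question.

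**What to change.** - **Section 4.A:** ask men in both arms, from baseline to week 8, not to eat blueberries or blueberry products and not to take berry or anthocyanin supplements, and otherwise to eat as usual.
- **Section 4.D:** state that blueberry and other berry intake will be reported by arm from the eight three-day food records.

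**Cost.** One instruction from the dietitian who already counsels each man, and one table from data already being collected. The downside is a minor restriction on an otherwise free-living diet, so the result would apply to men not otherwise eating blueberries. The report should say so.
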